Participants will be randomized to a MedDiet program or the currently offered American College of Obstetricians and Gynecologists (ACOG)-based dietary counseling program at Myers Park and North Park OBGYN Clinic(s) in Charlotte, North Carolina.

Duration of Study and Participating Site

This will be a multi-center study including Myers Park OB/GYN Clinic and North Park OB/GYN Clinic which are academic obstetrical practices providing prenatal care to a socially vulnerable and highly racial/ethnic diverse population. All new scheduled prenatal visits will be screened in Epic for eligibility by our research team.

We anticipate full completion of the study by July 2025.

Study population (Table 1)

Inclusion Criteria	Exclusion Criteria

• Viable singleton pregnancy in the first trimester (6 0/7- 16 6/7 weeks); includes twins reduced to singleton spontaneously or vanishing twin syndrome• BMI $\geq 25.0 \text{ kg/m}^2$; calculated by dividing maternal weight in kilograms by height in meters squared using a calibrated scale and standard metric measure (BMI calculator available at www.cdc.gov)• Confirmed intrauterine pregnancy by ultrasound exam (6-16 weeks)• Age 18 years or older• Primary language of English or Spanish	
• BMI $< 25.0 \text{ kg/m}^2$• Known pre-pregnancy diabetes• Hemoglobin glycosylated (A1C) $> 5.7\%$ at first prenatal visit• Pre-pregnancy hypertensive disease• Non-viable pregnancy• Known allergies to an essential component(s) of MedDiet• Inability to read or write in primary language• Mental incapacity to make medical decisions• Food insecurity

Sample Size

Since this is a pilot study, we aim to enroll 60 participants with 30 per study arm. Based on the patient population at Myers Park, we anticipate the following racial/ethnic breakdown of subjects.

Table 2 Anticipated Enrollment (all subjects will be female)

Race	Non-Hispanic	Hispanic	Total
Asian	1	0	1
Black or African American	15	0	15
White	6	36	42
More than One Race	2	0	2
Total	24	36	60

Methods and Intervention

- Fig 1 and Table 3 provide a detailed view of the study activities.
- With the purpose of overcoming language barriers, the dietary program was developed in English and Spanish. Multiple aids were created including practical educational tools, recipes, shopping list, and meal portion guidance to improve engagement and enhance sustainability.

Randomization and Study Groups:

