- Following informed consent and eligibility confirmation, subjects will be randomized in blocks of 4 using a single sequence computer-generated random number⁴⁰ to balance for baseline BMI category (overweight or obese Random allocation number assigned to MedDiet program (intervention group) or ACOG-based nutritional counseling (control group) will be in a sealed opaque envelope.
 - Subjects allocated to the ACOG-based Dietary Program (Control Group) will receive:
 - Following ACOG recommendation, routine counseling on healthy eating will be provided. This will include advice on the consumption of grains, fruits, vegetables, protein, and dairy foods recommended during pregnancy ([Nutrition During Pregnancy | ACOG](#))⁴¹ (www.myplate.gov). (Appendix A-F (English)/Appendix G-L (Spanish))
 - Diet adherence will be assessed using a Routine Diet Adherence Questionnaire (Appendix M (English)/Appendix N (Spanish)).
 - Six traditional healthy meals will be shipped by ModifyHealth LLC directly to the participant's home every 3 weeks between enrollment and until the subject is approximately 38 weeks pregnant.
 - Participants will receive canola oil and a healthy snack during their enrollment visit and during their routine 26-30 week prenatal visit
 - Subjects allocated to the MedDiet Program (Intervention Group) group will receive:
 - Counseling based on the principles of the traditional MedDiet²⁷ with a focus on a general change in diet instead of micronutrients or macronutrients. (Appendix O-P;SS-UU (English)/Appendix Q-R; VV-XX (Spanish))
 - Diet adherence will be assessed using a modified version of the validated MedDiet Adherence Questionnaire.³⁹ (Appendix S (English)/Appendix T (Spanish))
 - Six traditional MedDiet meals will be shipped by ModifyHealth LLC directly to the participant's home every 3 weeks between enrollment and until the subject is approximately 38 weeks pregnant.
 - Participants will receive olive oil and nuts during their enrollment visit and during their routine 26-30 week prenatal visit.

Baseline Visit:

- All subjects will participate in a 30-minute baseline Nutritional Assessment and Diet Counseling Session regardless of the arm they are randomized to. This will occur during their initial prenatal visit at 6-16 weeks of pregnancy. The following items will be covered in this visit:

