- Between 26-30 weeks, all subjects will have a total of 8 ml of blood drawn for the following tests:
 - C-reactive protein (CRP)
 - metabolic panel that includes glucose level
 - the lipid panel (total cholesterol, triglycerides, high-density lipoprotein (HDL) cholesterol, and low-density lipoprotein (LDL) cholesterol)
 - hemoglobin A1c

The blood sample collection form will be completed at each timepoint (Appendix Z)

- For each meal received from ModifyHealth, subjects will be asked to take share a photo (via REDCap using the subject's cell phone number or email, EPIC, or in-person) of the uneaten food.

Data on subjects' history and pregnancy/neonatal outcomes will be collected via EPIC:

- The following data will be collected from EPIC for all subjects
 - Medical history (Appendix HH (Spanish)/Appendix TT(English)))
 - Reproductive, and obstetric history including all prior pregnancy complications/outcomes and neonate outcomes (Appendix II (Spanish)/Appendix UU(English)))
 - Current pregnancy labs (Appendix JJ)
 - Current pregnancy, scans, complications, progress reports, clinic reports, hospital reports
 - Current pregnancy outcomes (Appendix KK)
 - Neonatal outcomes will be collected up to 6-weeks post-delivery including all birth data and complications (Appendix LL)
- Data regarding any adverse events will be collected on the Adverse Event form. (Appendix MM).
- Data collected on data collection forms (Appendix HH-LL) and then transferred to REDCap.

Fig 1. Overview and Intervention

[figure not shown]

Table 3

	Screening/ Enrollment/ Randomization		Between 20-24 weeks of pregnancy		Between 26-30 weeks of pregnancy		Between 34-38 weeks of pregnancy	
	Routine Diet	MedDiet	Routine Diet	MedDiet	Routine Diet	MedDiet	Routine Diet	MedDiet
Informed consent	X	X						
Inclusion/ Exclusion criteria	X	X						
Medical record release	X	X						
Medical, reproductive, & obstetric history*	X	X						

Nutrition (FIGO) checklist	X	X						
Food insecurity screening	X	X						
Diet information & handouts provided	X	X						
Diet and physical activity counseling	X	X	X	X	X	X	X	X
Blood draw for: 1. CRP 2. metabolic panel 3. Lipid panel 4. A1C	X	X			X	X		
MedDiet adherence screening				X		X		X
Routine Diet adherence screening			X		X		X	
6 meals delivered every 3 weeks	X	X	X	X	X	X	X	X
Olive oil and nuts provided		X				X		
Canola oil and healthy snack provided	X				X			
Exercise/food recall and general assessment questionnaire			X	X	X	X	X	X

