- **Cardiovascular parameters:** MedDiet is associated with reduction of blood pressure (BP) in non-pregnant adult overweight or obese women.⁵² Physiological changes of blood pressure (BP) during pregnancy are characterized by reduction of BP in the second trimester with return to the pre-pregnancy level late in the third trimester and postpartum period.⁵³ Heart rate (HR) increases by 20% to 25% over baseline during gestation.⁵⁴ Maternal BP and HR will be obtained by a calibrated automated oscillometric device during prenatal visits from the first to the third trimesters following the standardized technique established in our clinic. Trends of BP and HR throughout gestation will be compared among women allocated in the intervention and the control groups.
- **Cardiometabolic biomarkers:** Consumption of MedDiet is associated with lower levels of total cholesterol,⁵³ reduces insulin resistance preventing type 2 diabetes^{30,31} and GDM,^{34,36} and reduces markers of subclinical inflammation such as C-reactive protein (CRP).⁵⁵ Pregnancy is characterized by increased levels of total cholesterol, low-density lipoprotein (LDL), high-density lipoprotein (HDL), and triglycerides, especially in the second and third trimester,⁵⁶ and pregnancy is a state of increased insulin resistance.⁵⁷ There is limited knowledge about the effect of MedDiet on cardiometabolic biomarkers during pregnancy. Maternal lipid profile, random glucose level, hemoglobin A1C, and CRP levels will be compared at baseline (6-16

weeks) and at 26-30 weeks of gestation among participants in the intervention and the control groups. The labs will be obtained at the same time of scheduled blood draws for routine prenatal labs.

Analytical Plan

This is prospective randomized pilot study of sixty participants who will be randomly allocated in the MedDiet group or in the control group. Because this is a pilot study, a sample size was not calculated. Results will be analyzed initially using descriptive statistics. Comparison between groups will be done using chi square tests for proportions, and t-tests or ANOVA procedures for continuous variables. Regression analysis will be performed to identify independent outcome predictors. Other inferential statistical analysis will be conducted as appropriate.

Human Subjects Protection

Screening and Recruitment

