Approximately 30 new prenatal visits are scheduled in our clinic weekly and we anticipate 10 of those patients will be eligible. All pregnancy confirmation visits will be screened by a research member (PI, Co-PI, study coordinator) in Epic to establish eligibility. The following PHI will be collected for screening purposes:

- Name
- MRN
- Age
- BMI
- Diagnosis of pre-pregnancy diabetes
- Hemoglobin glycosylated (A1C) value at pregnancy confirmation visit
- Diagnosis of pre-pregnancy hypertensive disease
- Confirmation of viable singleton pregnancy
- Gestational age of pregnancy
- Primary language of English or Spanish
- Food allergies

Screening data will be entered into an Excel spreadsheet stored on a secure drive which only the research team will have access to.

At the first prenatal visit, women who meet inclusion/exclusion criteria will be presented a flyer (Appendix NN (English)/ Appendix OO (Spanish)) and invited to participate in the study. Eligibility will be confirmed following informed consent and the Eligibility Form will be completed (Appendix PP).

Informed Consent

At the first prenatal visit, women who meet inclusion/exclusion criteria will be invited to participate in the study. Signed informed consent (Appendix QQ (English)/Appendix RR (Spanish))) will be obtained from each subject by a member of the research team. If the

research member obtaining consent is not fluent in Spanish, an interpreter will be used. Consent will be obtained in a private room with a closed door in the clinic during the subject's initial prenatal visit. Participants will be fully informed about the nature of the study and the potential risks of the dietary intervention, anticipated to be minimal as this is a behavioral intervention.

Spanish Speaking Subjects

All study related materials will be available in both English and Spanish. Qualified and trained Spanish language medical interpreters will be used to communicate with Spanish language participants if the investigators are not proficient in speaking Spanish.

Confidentiality and Privacy

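### The biomarker comparison at 26-30 weeks uses neither the baseline value nor, for lipids, gestational age at the draw, so it gives up precision without being biased

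*Combined protocol and SAP*

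**What the plan says.** Under Outcomes (Cardiometabolic biomarkers), the protocol says "Maternal lipid profile, random glucose level, hemoglobin A1C, and CRP levels will be compared at baseline", given there as 6-16 weeks, and "at 26-30 weeks of gestation among participants in the intervention and the control groups". The Analytical Plan names "t-tests or ANOVA procedures for continuous variables". It adds a regression to find independent predictors of outcome, listing no covariates, and other inferential analyses as appropriate.

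On timing:
- Table 1 admits a "Viable singleton pregnancy in the first trimester (6 0/7- 16 6/7 weeks", and the Baseline Visit section places the session that includes the baseline draw with "This will occur during their initial prenatal visit at 6-16 weeks of pregnancy".
- The Trimester Visits section sets the second draw: "Between 26-30 weeks, all subjects will have a total of 8 ml of blood drawn for the following tests".
- Both draws are tied to routine prenatal labs, not to a fixed week.

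The biomarker paragraph also states: "Pregnancy is characterized by increased levels of total cholesterol, low-density lipoprotein (LDL), high-density lipoprotein (HDL), and triglycerides, especially in the second and third trimester". Gestational age appears among the screening items ("Gestational age of pregnancy"). A collection form (Appendix Z, contents not shown) is completed at each draw. Randomization is balanced on BMI category only.

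**The concern.** Estimating the preliminary effect on the cardiometabolic profile is the second of the secondary objectives, and the results are meant to support larger trials. What the pilot can supply is an estimate with an interval, and with 30 women per arm that interval is wide. A marker measured twice in the same woman is usually correlated with itself, so the baseline value is the most obvious means of narrowing it. A t-test at 26-30 weeks leaves it out.

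For lipids there is a second, smaller source of noise. By the plan's own account they rise with gestation, yet the baseline sample can be taken anywhere in an 11-week span. A baseline value from week 6 and one from week 16 then do not mean quite the same thing, which makes the baseline a somewhat poorer predictor of the later value.

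**Working it through.** The plan gives no precision or power figure for the biomarkers and says that no sample size was calculated, so there is nothing to reproduce. The check asks how much interval width the stated test gives up.

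**From the documents**
- 30 women per arm.
- Baseline window 6 0/7 to 16 6/7 weeks: 77 days, or 11.0 weeks.
- Second window 26 0/7 to 30 6/7: 35 days, or 5.0 weeks.

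**Assumed, for total cholesterol (the documents give none of these)**
- SD 35 mg/dL at a fixed gestational age.
- Within-woman correlation ρ of 0.6-0.8 at fixed gestational ages.
- Rise b of 2-5 mg/dL per week.
- Draw days uniform within each window.

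**Step 1: timing scatter.** SD = √((days² − 1)/12)/7. Baseline: √((77² − 1)/12)/7 = 3.18 weeks. Second draw: √((35² − 1)/12)/7 = 1.44 weeks.

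**Step 2: plain t-test at 26-30 weeks, b = 3.** Variance = 35² + 3² × 1.44² = 1225 + 19 = 1244. The 95% half-width is 2.00 × √(1244 × 2/30) = 18.2 mg/dL.

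**Step 3: add the baseline value, b = 3, ρ = 0.7.** Baseline variance = 1225 + 3² × 3.18² = 1316. The correlation actually seen between the two draws is r = 0.7 × 1225/√(1316 × 1244) = 0.67. The half-width is multiplied by √(1 − 0.67²) = 0.74, and by about 1.01 for the extra parameter, giving 0.75. So 18.2 becomes 13.6, about 25% narrower. In variance terms this matches a plain t-test with about 30/0.75² = 53 women per arm.

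The same formulas at the other settings (linear rise from week 6):

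| Rise (mg/dL per week) | Narrowing, ρ = 0.6 | Narrowing, ρ = 0.8 |
|---|---|---|
| 2 | 18% | 37% |
| 5 | 15% | 29% |

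**Step 4: add gestational age at both draws to the baseline-adjusted model.** Simulated trials of 30 per arm gave these further changes in half-width:

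| Shape of the rise | Further narrowing |
|---|---|
| Linear from week 6, b = 3, ρ = 0.7 | about 3% (13.6 to 13.2) |
| Linear from week 6, all settings | about −1% to +15% (top at b = 5, ρ = 0.8) |
| Flat until week 13 or 14, then rising | about −1% to +5% |

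At b = 3 and ρ = 0.7 the full model takes the half-width from 18.2 to 13.2, about 27%, of which about 25 points come from the baseline value. Adding only gestational age at the second draw to the plain 26-30 week comparison changes it by about −1% to +1%.

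**Step 5: cost if gestational age carries no information.** Two useless covariates multiply the half-width by about √(1 + 2/56) = 1.02, so the interval is some 1-2% wider.

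**Step 6: bias.** Timing is independent of arm by randomization. In 20,000 simulated trials with no arm effect, an unadjusted t-test on change from baseline, the analysis most exposed to timing, rejected in 4.8% and 5.0% of trials at two assumed slopes.

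**Step 7: time between draws.** Shortest: 26 0/7 − 16 6/7 = 9.1 weeks. Longest: 30 6/7 − 6 0/7 = 24.9 weeks.

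**The case against.** The best case for leaving the plan alone is that this is a secondary, preliminary objective in a pilot with no decision rule attached, that the t-test is valid, and that the regression sentence and the allowance for other analyses leave room for covariates. The validity and the low stakes stand. The room for covariates does not settle the matter: the regression is for finding predictors, names no covariate, and is not the stated between-arm comparison.

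Four stronger readings are tempting, and the documents do not support them.

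- *Uneven draw timing biases the arm comparison.* It does not, as step 6 shows.
- *Timing scatter is the main loss.* It would matter most for change from baseline, where gestational age could narrow the interval by up to 20% under a steep linear rise. But the plan states no change score; its natural reading is an arm comparison at each time point. A straight-line rise from week 6 also sits uneasily with the plan's statement that the rise is mainly in the second and third trimesters, since the protocol starts the second trimester at week 14.
- *Chance imbalance in enrollment week is a further problem.* Its standard error is 3.18 × √(2/30) = 0.82 weeks, so arms differ by a week or more in about 22% of trials. That is the same noise already counted in the interval, and it bears on change scores.
- *Adjusting for gestational age deals with unequal time on the diet.* If the effect grows over 9 to 25 weeks of exposure, that is effect modification, which main effects of gestational age do not model.

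**Conclusion.** The point holds as a modest, optional improvement. The stated comparison is unbiased but less precise than the plan's own data allow, chiefly because it sets aside the baseline value. Baseline adjustment narrows the interval by about 18-37% under a mild rise of 2 mg/dL per week and correlations of 0.6-0.8. With a steep linear rise of 5 mg/dL per week the figure is 15-29%, and gestational age then recovers part of the rest.

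The gestational-age terms alone are worth little in most settings, and their value depends on a rate and shape of rise that the documents do not give. The case for them is confined to the lipids: the plan gives no gestational trend for CRP or A1C. All the sizes rest on assumed correlations, SD and slopes, illustrated on total cholesterol. The gain from baseline adjustment would be smaller for any marker with a lower within-woman correlation.

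**What to change.** In the Analytical Plan, state that each biomarker at 26-30 weeks is compared between arms by a linear model (ANCOVA) with arm and the woman's baseline value, and that the adjusted mean difference is reported with its 95% confidence interval. For total cholesterol, LDL, HDL and triglycerides, also include gestational age at the baseline draw and at the 26-30 week draw. Fixing this in advance also prevents covariates from being chosen after an imbalance is seen.

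The cost is wording and up to three degrees of freedom, with an interval about 1-2% wider for the lipids if gestational age proves uninformative. No visit, sample or participant is added. Gestational age is listed only as a screening item, so its value at each draw has to be derived from the draw date; the sponsor should confirm that Appendix Z records that date. If variation in time on diet is of interest, it needs a separate, exploratory analysis.

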 - Subjects will complete an enrollment questionnaire to obtain demographic and baseline diet/physical activity information (Appendix U (English)/Appendix V (Spanish))
 - Subjects will complete a form for ModifyHealth so their free meals will be delivered to their home (Appendix VV (Spanish)/ Appendix WW (English))
 - Additional subject enrollment data will be collected by the enrolling research teammate regarding a history of eating disorders, tobacco/alcohol/substance use, insurance coverage, phone number, and email (Appendix W(Spanish)/Appendix SS (English)).
 - Subjects will complete the Federation of Gynecology and Obstetrics (FIGO)⁴² Nutrition Checklist (Appendix X (English)/Appendix Y (Spanish)). This is a validated tool used to assess the subject's quality of diet. It consists of six yes/no questions (www.figo.org) and at least one "no" response will be classified as a suboptimal diet.⁴²
 - All subjects will have a total of 8 ml of blood drawn for the following tests:
 - C-reactive protein (CRP) panel
 - metabolic panel that includes glucose level
 - the lipid panel
 - hemoglobin A1c

The blood sample collection form will be completed at each timepoint (Appendix Z)

- All subjects will receive dietary advice for the diet they have been randomized to by a registered dietitian with expertise in nutrition during pregnancy (ST, Co-I). (Appendix A-C; F (English)/Appendix G-;-L (Spanish) or Appendix O-P (English)/Appendix Q-R (Spanish))
 - Educational materials for each diet program such as recipes, shopping lists, and meal plans will be discussed, and the material will be printed for the participant's use at home. (Appendix A-F (English)/Appendix G-L (Spanish) or Appendix O-P; SS (English)/Appendix Q-R; VV (Spanish))
 - Routine counseling of physical activity and exercise based on ACOG recommendations (ACOG Committee Opinion No 804) will be provided. If there are no clinical contraindications, women will be encouraged to start with low intensity, short periods of exercise at least 4 times a week. (Appendix A-F (English)/Appendix G-L (Spanish) or Appendix O-P (English)/Appendix Q-R (Spanish))

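### Free improvement for secondary objective 2: state that the 26-30 week biomarkers will be compared by ANCOVA on the baseline values already being collected

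*Combined protocol and SAP*

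**What the plan says.** The Analytical Plan gives one general rule for comparing the arms: "Comparison between groups will be done using chi square tests for proportions, and t-tests or ANOVA procedures for continuous variables". It adds "Regression analysis will be performed to identify independent outcome predictors" and ends with "Other inferential statistical analysis will be conducted as appropriate". None of these sentences says whether a woman's own baseline value enters the comparison.

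The data for such an adjustment are planned. Under Baseline Visit: "All subjects will have a total of 8 ml of blood drawn for the following tests", followed by CRP, a metabolic panel with glucose, lipids and A1C. Under Trimester Visits: "Between 26-30 weeks, all subjects will have a total of 8 ml of blood drawn for the following tests", with the same four items. The schedule of activities marks the draw in both arms at both times.

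Under Outcomes, Cardiometabolic biomarkers, the plan says "Maternal lipid profile, random glucose level, hemoglobin A1C, and CRP levels will be compared at baseline" and again at 26-30 weeks, between the two groups. For blood pressure and heart rate it says "Trends of BP and HR throughout gestation will be compared among women allocated in the intervention and the control groups" and gives no method for several readings per woman.

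**The concern.** Secondary objective 2 is to estimate a preliminary effect on the cardiometabolic profile. The plan states that no sample size was calculated, so the usefulness of each biomarker estimate to a later trial depends largely on the width of its interval.

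The wording on biomarkers can be read in at least two ways. One is a separate between-arm test at each time. Its baseline half carries no information about the intervention, and its follow-up half ignores the baseline. The other is a comparison of changes, which is also what the group-by-time test of a two-time-point repeated-measures ANOVA amounts to. Under randomisation both give an unbiased comparison at follow-up, but they differ in precision and the plan does not choose. A third option, ANCOVA, uses the same data and is more precise than both over most plausible correlations. Leaving the choice open also allows it to be made after the results are known.

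**Working it through.** **Inputs from the documents.** 60 women, 30 per arm (Sample Size). No power, effect size, SD, dropout rate or correlation is stated, so there is no figure of the plan's own to reproduce.

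**Assumptions.** Two-sided 95% intervals; results in units of the SD of the 26-30 week value, with equal SD at both times; baseline to follow-up correlation r of 0, 0.3, 0.5 or 0.7; 30 evaluable women per arm, or 24 per arm (20% loss).

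**Formulas for the half-width, with n per arm.**

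- Unadjusted comparison at 26-30 weeks: t(0.975, 2n−2) × √(2/n).
- Change score: the unadjusted half-width × √(2(1−r)).
- ANCOVA on baseline: t(0.975, 2n−3) × √[(2/n)(1−r²)(1+1/(2n−4))]. The last factor charges for chance baseline imbalance, and the smaller degrees of freedom for estimating the slope.

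**Worked example, n = 30.**

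- Unadjusted: 2.002 × √(2/30) = 0.517.
- Change score, r = 0.5: 0.517 × √1 = 0.517.
- ANCOVA, r = 0.5: 2.002 × √(0.0667 × 0.75 × 1.0179) = 0.452. The ratio to unadjusted is 0.874, so about 13% narrower.

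**Results (half-width in SD).**

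| | r = 0 | r = 0.3 | r = 0.5 | r = 0.7 |
|---|---|---|---|---|
| 30 per arm, unadjusted | 0.517 | 0.517 | 0.517 | 0.517 |
| 30 per arm, change score | 0.731 | 0.612 | 0.517 | 0.400 |
| 30 per arm, ANCOVA | 0.522 | 0.498 | 0.452 | 0.373 |
| ANCOVA / unadjusted | 1.009 | 0.963 | 0.874 | 0.721 |
| 24 per arm, unadjusted | 0.581 | 0.581 | 0.581 | 0.581 |
| 24 per arm, change score | 0.822 | 0.688 | 0.581 | 0.450 |
| 24 per arm, ANCOVA | 0.588 | 0.561 | 0.509 | 0.420 |

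A simulation of 10,000 trials per correlation at 30 per arm gave the same ratios: 1.009, 0.963, 0.874 and 0.721.

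**Equivalent sample size.** At r = 0.3, 0.5 and 0.7, ANCOVA with 30 per arm is as precise as an unadjusted comparison with about 32, 39 and 58 per arm. From n/[(1−r²)(1+1/(2n−4))], for example: 30/(0.75 × 1.0179) = 39.3.

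**Break-even.** ANCOVA and the unadjusted comparison are equally wide when (1−r²)(1+1/56) × [t(0.975, 57)/t(0.975, 58)]² = 1, which gives r of about 0.14.

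**Adding BMI category.** If neither covariate predicts the outcome, the width ratio is about √(1+2/55) × t(0.975, 56)/t(0.975, 58) = 1.018 × 1.001 = 1.019, a cost of about 2%.

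**The case against.** The strongest reply is that the plan already permits ANCOVA. ANOVA procedures, regression and the closing as-appropriate clause all leave room for it, so an analyst could fit it without departing from the plan. That is right, and it limits the point to specification. The same clause equally permits the less precise options, including a change score that at r = 0.3 is 18% wider than ignoring the baseline altogether (0.612/0.517 = 1.18).

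A second reply is that the gain depends on a correlation the documents do not give. This also stands. The baseline window of 6-16 weeks is wide, glucose is sampled at random, and the range of A1C is restricted by the exclusion above 5.7%. Any of these could keep the correlation low. But the stakes are uneven: the loss is about 1% to 2% in width at worst, against a gain of 13% at a correlation of 0.5.

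A third reply is that this is a pilot and the objective is secondary. True; it limits the importance of the point and does not remove it.

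Two stronger readings are tempting. A reader might infer that the plan rules out baseline adjustment or that its biomarker comparison is biased. Neither follows: adjustment is left open, and in a randomised comparison the unadjusted difference is unbiased. A reader might also infer that the blood pressure and heart-rate comparison will have a wrong error rate or will miss a mid-pregnancy effect. The documents name no model, number of readings or trend shape, so no such rate can be attached to this plan. All that can be said is that no method for repeated readings is stated.

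**Conclusion.** The point holds as a low-cost improvement in the precision and pre-specification of secondary objective 2. It is certain that the plan specifies no use of the baseline value. The size of the benefit is conditional: ANCOVA probably narrows the intervals, and does so on average once the correlation exceeds about 0.14. The figures rest on the assumed correlations, equal SDs at the two times and an outcome suited to a linear model; with an assumed 20% loss the relative gains are nearly the same. The benefit will differ by analyte.

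**What to change.** Add to the Analytical Plan, for each biomarker:

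- The MedDiet minus control difference at 26-30 weeks will be estimated by ANCOVA, adjusting for that analyte's baseline value and for BMI category (the factor the randomisation is meant to balance), and reported with a 95% confidence interval.
- Skewed analytes will be analysed on the log scale.
- Baseline values will be shown by arm descriptively, without a test.
- The number of women with both draws will be reported by arm.

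Since the baseline session follows randomisation, confirm that the first draw precedes any study food, so that the covariate cannot be affected by the arm.

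For blood pressure and heart rate, add a sentence naming the method for repeated readings.

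The biomarker change costs analysis wording only: both draws are already planned for all women, and no visit, sample or participant is added.
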